11.4.3.4 Part C (MAD) - Accumulation

For each dose level, log-transformed C_{\max} and $AUC_{0-\tau}$ (only applicable if non-q.d. dosing regimen is implemented) values on Day 1 and Final Dosing Day (Day 10) will be subjected to an ANOVA with study day as a fixed effect and subject as a random effect. For comparison, point estimates and 90% CIs for the difference between Day 10 and Day 1 will be constructed using the residual mean square error obtained from the ANOVA for each dose level. The point and interval estimates will then be back transformed to give estimates of the ratios of the geometric LSMeans and corresponding 90% CIs. In addition, estimated geometric LSMeans and corresponding 95% CIs will be presented for each study day.

The geometric LSMean ratios and corresponding 90% CIs for C_{\max} and $AUC_{0-\tau}$ will be represented graphically (a plot with error bars) with all dose levels on one graph, one graph per parameter. On the same graph, points indicating individual within-subject ratios will be presented.

Statistical analysis of PK parameters will be performed using the PK set.

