3.1 OVERVIEW

This is a phase I, randomised, double-blind, placebo-controlled study to investigate the safety, tolerability, and PK of AX-158 in healthy male participants following single (Part A) and multiple (Part C) ascending doses including food effect (Part B).

The study will be conducted in three parts:

Part A

Part A (SAD) will enrol up to 8 participants per cohort randomised (3:1) to receive AX-158 or placebo. Part A will follow a single ascending dose (SAD) design with all participants receiving one dose of AX-158 (or placebo) in the fasted state.

This part will be conducted in up to 34 participants (8 participants in cohorts 1 and 5, 6 participants in cohorts 2, 3 and 4). An additional two cohorts of up to eight (8) participants each (up to 16 additional participants total) may be investigated if required.

Part B

Part B (Food Effect) will be conducted in up to 8 participants in a cross-over manner; each participant will receive AX-158 in the fed and fasted state.

This part will be conducted in up to 8 participants in a cross-over manner.

Part C

Part C (MAD) will enrol up to 8 participants per cohort randomised to (3:1) to receive AX-158 or placebo. Part C will follow a multiple ascending dose (MAD) design with participants receiving AX-158 (or placebo) once daily for 10 consecutive days, in a fed or fasted state (depending on the outcome of the Part B (Food Effect)). Doses, dosing duration and dose regimen (i.e., q.i.d., b.i.d., t.i.d.) of AX-158 and matching placebo for Part C may be modified based on all available safety, tolerability, and PK data and applied to additional MAD cohorts.

This part will be conducted in up to twenty-four (24) participants (3 cohorts of up to 8 participants). An additional two cohorts of up to eight (8) participants each (up to 16 additional participants total) may be investigated if required.

Duration of study:

- Part A: approximately 6 weeks for each individual (from the screening to post-study follow-up).
- Part B: approximately 8 weeks for each individual (from the screening to post-study follow-up).
- Part C: approximately 7 weeks for each individual (from the screening to post-study follow-up).

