4.2 SECONDARY VARIABLES

The secondary plasma pharmacokinetic (PK) endpoints for this study are as follows:

- C_{\max} Maximum observed concentration

Version: 3.0
Document Title: SAP Template - Phase 1
Document Number: TEMP-00109
Previous Document Number: STATt008

• T_{max}	Time to maximum observed concentration
• T_{lag}	The delay in achieving T_{max} (only in Part B)
• k_{el}	Elimination rate constant
• $t_{1/2}$	Terminal elimination half-life
• AUC_{0-24}	Area under the concentration-time curve (AUC) from the time of dosing to 24 hour post dose
• $AUC_{0-\tau}$	If part C dosing is not q.d.
• AUC_{0-t}	Area under the concentration-time curve (AUC) from the time of dosing to the time of the last measurable concentration
• $AUC_{0-\infty}$	AUC extrapolated to infinity
• $AUC_{\% \text{ extrapolated}}$	Residual area
• CL/F	Apparent total body clearance
• Vz/F	Apparent volume of distribution

The secondary urine PK endpoints for Part C of this study are:

• A_e	Amount and cumulative amount of dose excreted in urine over each collection interval
• $A_e\%$	% and cumulative % of dose excreted in urine over each collection interval
• CL_R	Renal clearance

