AUC_{0-24} ($\text{h}^*\mu\text{g/mL}$)	Area under the concentration-time curve (AUC) from the time of dosing to 24 h post-dose	AUC measured from the concentration at time of dosing to 24 hours post dose. The AUC is computed using the linear up-log down trapezoidal rule.	AUC0-24
$AUC_{0-\tau}$ ($\text{h}^*\mu\text{g/mL}$) (only required if non-q.d. dosing regimen)	Area under the plasma concentration-time curve (AUC) from the time of dosing to $<X>$ hours (dosing interval) after the Day $<X>$ dose.	AUC measured from the concentration at time of dosing to the concentration at $<X>$ hours. The AUC is computed using the linear up-log down trapezoidal rule.	AUC_TAU

Part C on Final Dosing Day:

Pharmacokinetic Parameter and Unit	Definition	Computation	WinNonlin Parameter Name
C_{max} ($\mu\text{g/mL}$)	Maximum concentration.	Maximum observed concentration, occurring at T_{max} . If not unique, then the first maximum is used.	Cmax
T_{max} (h)	The time to maximum observed concentration.	Time of maximum observed concentration. If the maximum observed concentration is not unique, then the first maximum is used.	Tmax

Pharmacokinetic Parameter and Unit	Definition	Computation	WinNonlin Parameter Name
λz (1/h)	Elimination rate constant.	First order rate constant associated with the terminal (log-linear) portion of the curve. Estimated by linear regression of time vs. log concentration; the regression analysis should contain data from at least 3 different time points in the terminal phase	lambda_z
$t_{1/2}$ (h)	Terminal elimination half-life.	$= \ln(2) / \lambda z$	HL_Lambda_z
AUC_{0-24} (h* μ g/mL)	Area under the concentration-time curve (AUC) from the time of dosing to 24 h post-dose	AUC measured from the concentration at time of dosing to 24 hours post dose. The AUC is computed using the linear up-log down trapezoidal rule.	AUC0-24
$AUC_{0-\tau}$ (h* μ g/mL) (only required if non-q.d. dosing regimen)	Area under the plasma concentration-time curve (AUC) from the time of dosing to 24 hours (dosing interval) after the Day 10 dose.	AUC measured from the concentration at time of dosing to the concentration at 24 hours. The AUC is computed using the linear up-log down trapezoidal rule.	AUC_TAU

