11.4.3.2 Part C (MAD) - Dose-Proportionality/Independence

Dose-Proportionality

For Day 1 and Final Dosing Day (Day 10), dose proportionality will be assessed by performing a regression analysis of the log-transformed C_{\max} , AUC_{0-tau} and AUC_{0-inf} (Day 10 only) values versus the log-transformed dose using the power model with a fixed effect for log (dose). For each parameter, a point estimate and 95 % CI will be calculated for the slope of the regression line.

Version: 3.0
Document Title: SAP Template - Phase 1
Document Number: TEMP-00109
Previous Document Number: STATt008

The power model is defined as:

$$\log_e(C_{\max}, AUC_{0-t}, AUC_{0-\infty}) = \alpha + \beta \log_e(\text{Dose}) + \varepsilon,$$

where α is the intercept, β is the slope and ε is the error term.

Geometric LSMeans and associated 95% CIs along with individual subject values for the derived pharmacokinetic parameters C_{\max} , AUC_{0-t} and $AUC_{0-\infty}$ will be presented graphically versus dose with each parameter presented on a separate plot.

Dose Independence

For Final Dosing Day (Day 10), dose independence will be assessed for $t^{1/2}$ and CL/F by performing a regression analysis of the untransformed parameters versus dose with a fixed effect for dose. For each parameter, a point estimate and corresponding 95 % CI will be calculated for the slope of the regression line.

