Source Listing: 16.2.5.2; Produced: yyyy-mm-ddThh:mm Page x of y

Treatment: single dose of AX-158 capsule or placebo in the fasted state.

Results obtained using a regression analysis on log-transformed values versus log-transformed dose using the power model.

Programming Note: A similar table will be presented for Part C (MAD), including C_{\max} and $AUC_{0-\tau}$ results for Day 1 and Day 10 and $AUC_{0-\infty}$ results for Day 10, with treatment footnote as presented in Table 14.3.1.1.

AX-158-101
Table 14.4.2.3
Summary of Statistical Analysis of Plasma AX-158 Dose Independence - Part A (SAD)
PK Set

Parameter	LSMeans (95% CI)					
	Cohort 1: AX-158 5 mg (N=X)	Cohort 2: AX-158 10 mg (N=X)	...	Cohort 5: AX-158 50 mg (N=X)	Intercept	Slope (95% C.I.)
$t_{1/2}$ (<units>)	x.xx (x.xx, x.xx)	x.xx (x.xx, x.xx)	x.xxxx	x.xxxx (x.xxxx, x.xxxx)
CL/F (<units>)	x.xx (x.xx, x.xx)	x.xx (x.xx, x.xx)	x.xxxx	x.xxxx (x.xxxx, x.xxxx)

Source Listing: 16.2.5.2; Produced: yyyy-mm-ddThh:mm - Page x of y

Treatment: single dose of AX-158 capsule or placebo in the fasted state.

Results obtained using a fixed effects ANOVA on non-transformed data with a fixed effect of dose.

Programming Note: A similar table will be presented for Part C (MAD), including results for final dosing day (Day 10), with treatment footnote as presented in Table 14.3.1.1.

AX-158-101

Figure 14.4.2.1

Dose Response of Derived Plasma AX-158 Pharmacokinetic Parameters - Part A (SAD)
PK Set

< parameter (<units>) >

Figure Specifications

Procedure: SGPLOT

By: Parameter, one parameter per page

x axis: Dose
x axis: Label: AX-158 Dose (mg)
x axis: values: All dose levelsY axis Geometric LSMeans and 95% CI for C_{max} , AUC_{0-t} and AUC_{0-inf} ; LSMeans and 95% CI for $t_{1/2}$ and CL/F - overlaid with individual subject valuesY axis Label: Geo. LSMeans (95% CI) for C_{max} , AUC_{0-t} and AUC_{0-inf}
LSMeans (95% CI) for $t_{1/2}$ and CL/F
Y axis values: As Appropriate

Legend: Not Applicable

Source Listing: 16.2.5.2; Produced: yyyy-mm-ddThh:mm Page x of y

Treatment: single dose of AX-158 capsule or placebo in the fasted state.

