Summary of Statistical Analysis of Plasma AX-158 Steady State - Part C (MAD)
PK Set

Treatment	AX-158 Trough Concentration (<units>)		Geometric LSMean Ratio (90% CI)
	Geometric LSMeans (95% CI)	Day 10	
	Day 5	Day 10	Day 10/Day 5
Cohort <X>: AX-158<X> mg (N=x)	xxx (xx.xx, xx.xx)	xxx (xx.xx - xx.xx)	x.xx (x.xx - x.xx)
Cohort <X>: AX-158<X> mg (N=x)	xxx (xx.xx, xx.xx)	xxx (xx.xx - xx.xx)	x.xx (x.xx - x.xx)

Source Listing: 16.2.5.1; Produced: yyyy-mm-ddThh:mm Page x of y
Treatment: once daily dosing of AX-158 or placebo in a <fasted/fed> state for 10 days, with the final dose administered on the morning of Day 10.
Results obtained using a mixed effects ANOVA on log-transformed data with a fixed effect of study day and a random effect of subject.

AX-158-101

Figure 14.4.2.3

Steady State Least Squares Geometric Mean Ratios and 90% CIs of Plasma AX-158 Concentration Data - Part C (MAD)
PK Set

<Treatment>

Figure Specifications

Plot type: Least squares geometric mean ratios (with 90% CI) overlaid with individual subject ratios.

By: Treatment and comparison - Day 10/Day 5 displayed on one plot, one plot per treatment.

x axis: Parameter

x axis: Label: Comparison

x axis: values: Day 10/Day 5

Y axis: Least squares geometric mean ratio and 90% CI, with individual subject ratios

Y axis Label: Ratio (90% CI)

Y axis values: As appropriate

Legend: N/a

Source Listing: 16.2.5.1; Produced: yyyy-mm-ddThh:mm - Page x of y

Treatment: once daily dosing of AX-158 or placebo in a <fasted/fed> state for 10 days, with the final dose administered on the morning of Day 10.

Results obtained using a mixed effects ANOVA on log-transformed data with a fixed effect of study day and a random effect of subject.

AX-158-101
Table 14.4.2.6
Summary of Statistical Analysis of Plasma AX-158 Accumulation - Part C (MAD)
PK Set

Dose Level	Parameter	n	Geometric LSMeans (95% CI)		Geometric LSMean Ratio (90% C.I.)
			Day 1	Day 10	
Cohort <X>: AX-158 <X> mg (N=x)	C_{\max} (<units>)	x	x.xx (x.xx, x.xx)	x.xx (x.xx, x.xx)	x.xx (x.xx, x.xx)
	$AUC_{0-\tau}$ (<units>)	x	x.xx (x.xx, x.xx)	x.xx (x.xx, x.xx)	x.xx (x.xx, x.xx)
Cohort <X>: AX-158 <X> mg (N=x)	C_{\max} (<units>)	x	x.xx (x.xx, x.xx)	x.xx (x.xx, x.xx)	x.xx (x.xx, x.xx)
	$AUC_{0-\tau}$ (<units>)	x	x.xx (x.xx, x.xx)	x.xx (x.xx, x.xx)	x.xx (x.xx, x.xx)

Source Listing: 16.2.5.7; Produced: yyyy-mm-ddThh:mm - Page x of y

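### With Part C dosed once daily, the SAP text leaves no AUC in the accumulation ANOVA or the Day 1 dose-proportionality regression, while the shells still ask for one

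*SAP*

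**What the plan says.** SAP 3.1 describes Part C participants as "receiving AX-158 (or placebo) once daily for 10 consecutive days". A change of regimen is allowed, but once daily is the plan.

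Three SAP sections restrict AUC0-tau to other regimens:

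- Section 4.2 lists it as a secondary variable with the condition "If part C dosing is not q.d".
- The Part C tables in 11.4.2, for Day 1 and for the Final Dosing Day, mark it "only required if non-q.d. dosing regimen".
- Section 11.4.3.4 names Cmax and AUC0-tau for the accumulation ANOVA and adds that AUC0-tau is "only applicable if non-q.d. dosing regimen is implemented".

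The Part C proportionality sentence in 11.4.3.2 names Cmax, AUC0-tau and AUC0-inf, with AUC0-inf limited to Day 10. The model line and plot sentence below it name Cmax, AUC0-t and AUC0-inf.

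The shells carry no such restriction. The Part C note to Table 14.4.2.2 asks for Cmax and AUC0-tau "results for Day 1 and Day 10 and" AUC0-inf for Day 10, and the note to Figure 14.4.2.1 does the same. Table 14.4.2.6 has an AUC0-tau row for every dose level and Figure 14.4.2.4 has an AUC0-tau plot. Both stand over a footnote that describes once-daily treatment.

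**The concern.** For the regimen actually planned, the text and the shells specify different outputs, and the programmer has to choose between them. Following the text, the multiple-dose PK objective gets no AUC accumulation ratio and no Day 1 AUC slope. Following the shells, four outputs need a parameter that the derivation rules do not provide under once-daily dosing.

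The gap falls on a metric that the study relies on: the exposure limits in protocol 8.5 and 10.3.4 are set for Cmax and AUC0-24. On Day 10 the regression sentence keeps only AUC0-inf among the AUCs. That parameter depends on the terminal slope and is not reported if the lambda-z criteria in SAP 11.4.2 are not met.

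**Working it through.** The plan states no figure to reproduce. The check compares, for each Part C analysis, the parameters it names with the parameters derived on that day under once-daily dosing.

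**Derived under once-daily dosing (SAP 11.4.2)**

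- Day 1: Cmax, Tmax, AUC0-24.
- Final Dosing Day: Cmax, Tmax, lambda-z, t1/2, AUC0-24, AUC0-t, AUC0-inf, AUC%extrap, CL/F, Vz/F.

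**Usable = named and derived.** Accumulation needs the parameter on both days.

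| Analysis | Named in SAP sentence | Usable, once daily | Usable, other regimen |
|---|---|---|---|
| Accumulation (11.4.3.4) | Cmax, AUC0-tau | Cmax | Cmax, AUC0-tau |
| Proportionality, Day 1 (11.4.3.2) | Cmax, AUC0-tau | Cmax | Cmax, AUC0-tau |
| Proportionality, Day 10 (11.4.3.2) | Cmax, AUC0-tau, AUC0-inf | Cmax, AUC0-inf | all three |

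The text is therefore complete only for a regimen that is not planned. Reading the 11.4.3.2 model line instead does not help on Day 1: of Cmax, AUC0-t and AUC0-inf, only Cmax is derived that day.

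**Counts for three dose levels, once daily**

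- Accumulation ratios = dose levels × parameters. Text: 3 × 1 = 3. Table 14.4.2.6: 3 × 2 = 6.
- Day 1 slopes, one per parameter. Text: 1. Table 14.4.2.2 Part C note: 2.
- Day 10 slopes. Text: 2, or 3 if AUC0-t is taken from the model line. Part C note: 3.

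**With AUC0-24 in place of AUC0-tau.** Protocol 10.11.8 gives the planned interval as 0 to 24 h, so the two are the same area. Both are computed with the same trapezoidal rule in SAP 11.4.2. AUC0-24 is derived on both days, so text and shells then agree at 6 ratios, 2 Day 1 slopes and 3 Day 10 slopes.

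**How much AUC accumulation would go unestimated.** The documents give no human half-life, so this cannot be derived from them. As an illustration only, assume one compartment, first-order absorption with ka = 1 per hour, and ten doses 24 h apart. The concentration after dose n is then proportional to the sum over j = 0 to n−1 of exp(−k(t+24j)) − exp(−ka(t+24j)), with k = ln 2 / half-life. Day 10 / Day 1 ratios:

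| Assumed half-life (h) | AUC0-24 ratio | Cmax ratio |
|---|---|---|
| 6 | 1.08 | 1.08 |
| 12 | 1.36 | 1.36 |
| 24 | 2.06 | 2.04 |
| 48 | 3.43 | 3.37 |

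The missing ratio could be trivial or above 3. In this simple model Cmax tracks it closely, but that agreement is a feature of the assumed model.

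**The case against.** The strongest reply is that this is labelling. With a 24 h interval AUC0-tau is AUC0-24, and the Final Dosing Day row for AUC0-tau already reads "from the time of dosing to 24 hours (dosing interval) after the Day 10 dose". A PK programmer could fill the AUC0-tau rows with AUC0-24 from both days. The equality stands, but for accumulation the substitution would go against the explicit statement in 11.4.3.4 that the AUC comparison applies only to other regimens.

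Second, for Day 1 proportionality the removal is indirect. Section 11.4.3.2 sets no condition of its own, and the condition in 11.4.2 says the parameter is not required, which is weaker than forbidden. The general proportionality paragraph in 11.4.3 names AUC0-24 and has no part label. This stands in part: the Day 1 gap follows from the derivation rules, not from the regression sentence. But Part C has its own section and shell note, both omit AUC0-24, and the general paragraph says nothing about accumulation.

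Third, text against shells is too tidy a contrast, because the plot sentence in 11.4.3.4 itself asks for AUC0-tau ratios without the condition. That is correct, and it adds to the contradiction.

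Fourth, the supplied protocol is weak support. Its accumulation paragraph (10.11.8) includes an AUC with no regimen condition, but its endpoint list (10.11.2) restricts AUC0-tau in the same way, so V4.0 has the same gap. The SAP was written to V5.0, which is not available here. The AUC0-t printed in the protocol's accumulation paragraph and in SAP 11.4.3.2 may also be a tau lost in PDF conversion. The conclusion rests on neither.

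Finally, this is a secondary objective without formal testing, and the SAP lets layouts change and alternative methods be documented in the study report. That limits the severity, but it would defer the choice until data are in hand.

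**Conclusion.** The point holds. Under the planned once-daily regimen, the SAP's rules leave Cmax alone in the accumulation ANOVA and Cmax alone in the Day 1 proportionality regression, while four shells require an AUC that those rules do not derive. The shortfall in the text is 3 of 6 accumulation ratios, 1 of 2 Day 1 slopes and 1 of 3 Day 10 slopes. These counts assume three cohorts at distinct dose levels, once-daily dosing, and the 11.4.2 conditions applied as written.

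This should be fixed before database lock, but it does not threaten the study. AUC0-24 is still summarised for Day 1 and Day 10 in Table 14.4.2.1, and the Cmax accumulation and Day 10/Day 5 trough analyses are unaffected.

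**What to change.** Adopt one rule and apply it throughout: AUC0-24 on Day 1 and Day 10 when dosing is once daily; AUC0-tau, with the same interval on both days, otherwise.

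- In 11.4.3.4, replace the parenthesis with this rule and bring the plot sentence into line.
- In 11.4.3.2, apply it to the regression sentence and correct the model line and plot sentence, which now show AUC0-t. Keep AUC0-inf on Day 10.
- Apply it to the Part C notes for Table 14.4.2.2 and Figure 14.4.2.1, and to Table 14.4.2.6 and Figure 14.4.2.4.
- In 11.4.2, change the Final Dosing Day definition of AUC0-tau from a fixed 24 hours to the actual dosing interval, as the Day 1 row already does with a placeholder. Otherwise a ratio under another regimen could compare unequal intervals.

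The cost is SAP and shell wording. AUC0-24 is already derived on both days, so no sample or parameter is added.

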11.5 PD ANALYSES

Not applicable.

11.6 SAFETY ANALYSES

11.6.1 Adverse Events

All adverse events (AEs) will be coded using the Medical Dictionary for Regulatory Activities (MedDRA) dictionary version 24.1.

All AEs, including those which occurred prior to the first treatment administration, will be listed. Only treatment emergent adverse events (TEAEs), i.e., existing conditions that worsen or events that occur during the course of the study after administration of study drug, will be included within the summary tables. AEs that occur intermittently will be reported as separate events.

Part A and Part C:

An AE will be assigned to treatment if it starts on or after dosing. Where there are only partial dates/times recorded for an adverse event, the adverse event will be assigned to treatment if it cannot be ruled out based on the partial information.

Part B:

An AE will be assigned to the most recent treatment if it starts on or after the corresponding dose. Where there are only partial dates/times recorded for an adverse event, the adverse event will be assigned to every treatment where it cannot be ruled out based on the partial information.

An overall summary of AEs will be produced including the number of TEAEs; the number and % of subjects reporting at least 1 TEAE, serious TEAE (where SAE is reported as 'Yes'), TEAE leading to withdrawal from the study (Action recorded as 'Study Drug Discontinued'), TEAE leading to death (Outcome recorded as 'Fatal'); the number and % of subjects reporting TEAEs by severity and relationship to study drug. A subject with multiple occurrences of any AE is counted only once at the maximum level of severity or the strongest relationship to study drug.

The number of TEAEs and the number and % of subjects reporting at least 1 TEAE will be tabulated by system organ class (SOC) and preferred term (PT). A subject reporting multiple episodes of a particular AE within a treatment period will only contribute 1 count towards the corresponding SOC and PT.

In order to highlight the most frequently reported TEAEs, the number of TEAEs and the number and % of subjects reporting at least 1 TEAE will be tabulated by PT in order of descending frequency such that AEs reported by the greatest number of subjects are presented first. A subject reporting multiple episodes of a particular AE will only contribute 1 count towards the corresponding PT.

In addition, the number and % of subjects reporting TEAEs will be tabulated by maximum severity and strongest relationship to study drug. For the summary of TEAEs by severity, if a subject has multiple events occurring within the same SOC or PT the event with the highest severity will be counted. Similarly, for TEAEs by relationship to study drug, if a subject has multiple events occurring within the same SOC or PT, the event with the strongest relationship to study drug will be counted.

AEs will be listed by treatment. For any adverse event occurring prior to first administration of study drug, treatment will be described as 'Prior to Treatment'.

The derived variables, 'Time from Dose' and 'Duration' will be presented where full date and time are present. If partial dates are present for any parameter required in the calculation, the variable will not be populated. The following will be used to calculate the variables:

Duration (dd:hh:mm): (Date/Time of Resolution - Date/Time of Onset) + 1 minute;

Time from Dose (dd:hh:mm): (Date/Time of Onset - Date/Time of Start of Dose).

The following will be presented in listing format within the data summaries:

- Serious Adverse Events – If there are none present, the listing will be produced stating: 'No subjects experienced any serious adverse events.'
- Adverse Events which Led to Withdrawal – If there are none present, the listing will be produced stating: 'No subjects experienced any adverse events that led to withdrawal'.
- Adverse Events Leading to Death – If there are none present, the listing will be produced stating: 'No subjects experienced any adverse events that led to death.'

Adverse event data will be listed and summarised using the Safety Set.

